5.4. Patient Disposition

Patient disposition includes the description of patient status at major milestone decisions in the study, as well as the patient analysis populations.

Patient study status will be summarized by treatment group and overall for the study (screened patients, screen failures, and non-randomized but treated patients only). Summaries will provide the frequency (and percentage as applicable) of patients that met the criteria for the variables described in Section 4.4. Exception listings will be generated for any subject treated but not randomized, randomized but not treated, and treated differently than randomized.

Patient analysis populations will be summarized by treatment group, depicting frequencies (and percentages) of patients that met the criteria for each population described in Section 3.

5.5. Extent of Study Treatment Exposure and Compliance

The extent of study treatment exposure and study compliance parameters for the treatment period described in Section 4.5 will be assessed and summarized by treatment group, for patients in the safety population.

5.5.1. Exposure to Investigational Product

Study treatment exposure for the treatment period will be descriptively summarized for the treatment duration and total number of injections as described in Section 4.5. Treatment duration will be summarized using the number of patients with data, mean, SD, median, minimum and maximum. Categorized 4-week intervals of treatment duration will be summarized descriptively by counts and percentages.

The incidence of premature study treatment discontinuation (irrespective of the reason) and premature treatment discontinuation due to AEs will be presented graphically by treatment group in the safety population using the Kaplan-Meier method.

Patient Up-titration

The number and percentage of patients with an up-titration in the Praluent group will be described. Patients with an up-titration are defined as up-titrated according to IVRS/IWRS Week 12 transaction with at least one injection of alirocumab 150 mg following the up-titration decision.

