If any clinically significant signal is detected and further characterization is needed or for AEs of clinical interest, selected TEAEs will be analyzed using a time-to-event approach (Kaplan-Meier methodology) to account for the differential exposure time in all patients. Time from the first dose of study drug to the first occurrence of the event will be calculated (only the first event will be counted). Patients without any event will be censored at the end of the TEAE period. Kaplan-Meier curves will be provided.

Death

The following death summaries will be generated:

- Number (%) of patients who died by study period (TEAE and post-study) summarized on the safety population by treatment received
- Death in nonrandomized patients or randomized and not treated patients
- TEAE leading to death (death as an outcome on the AE e-CRF page as reported by the investigator) by (at least) SOCs sorted by internationally agreed order, and PTs sorted by decreasing frequency in the Praluent group, showing the number (n) and percentage (%) of patients

Drug-Induced Liver Injury

Liver function tests, namely ALT, AST, alkaline phosphatase, and total bilirubin, are used to assess possible drug-induced liver toxicity. The proportion of patients with potentially clinically significant abnormal values (PCSA) at any post-baseline visit by baseline status will be displayed by treatment group for each parameter. A graph of distribution of peak values of ALT versus peak values of total bilirubin will also be presented (note that the ALT and total bilirubin values are presented on a logarithmic scale). The graph will be divided into 4 quadrants with a vertical line corresponding to 3 x upper limit of normal (ULN) for ALT and a horizontal line corresponding to 2 x ULN for total bilirubin.

The incidence of liver-related AEs will be summarized by treatment group. The selection of PTs will be based on a standardized MedDRA query hepatic disorder. Time to liver-related treatment discontinuation and time to liver death may also be provided based on the hepatic disorder standardized MedDRA query.

Neurocognitive Events of Special Interest:

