2.2. Sample Size and Power Considerations

To demonstrate the noninferiority of the Praluent 75 mg Q2W/up-titrate 150mg Q2W dose regimen relative to placebo for the primary endpoint of mean change in Spatial Working Memory (SWM) strategy z-score from baseline to week 96, the sample size for this study is calculated to be 1085 patients per treatment group. This sample size is based on the noninferiority margin of 0.2 for the primary outcome measure. Specifically, a worsening in the SWM strategy z-score of 0 to 0.2 at the group level (small effect size) would not be considered clinically meaningful. Whereas a worsening of 0.3 to 0.5 (or greater), a small-to-medium effect size, might be considered clinically relevant, indicating increased cognitive impairment (Roiser 2015). Therefore, a noninferiority margin of 0.2 on the SWM strategy z-score change from baseline is a conservative estimate of the largest clinically meaningless mean difference between Praluent and placebo treatment groups. Additionally, the assumed mean difference between the treatment groups is 0 and the standard deviation is 1.0 (the standard deviation is obtained from the Cambridge Cognition internal normative data). To achieve 95% power using a 2-sided 95% confidence interval (CI) approach (2-sided alpha=0.05), the sample size is calculated to require 651 patients per treatment group. Assuming dropout rate of 20% in the first year and 25% in the second year, the sample size is increased to 1085 patients per treatment group.

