- All TEAEs by treatment group regardless of relationship in one column and, in the same table a second column with TEAEs related to alirocumab according to investigator's opinion by primary SOC, HLGt, HLT and PT;
- All TEAEs by maximal severity (i.e., mild, moderate or severe), presented by primary SOC and PT, sorted as defined above;
- The event rate per patient-year (the number of patients with an event in question divided by total patient-years) will be provided for all TEAEs by SOC and PT. For a patient with event, patient year is censored at time of first event; for patient without event, it corresponds to length of TEAE period;
- Kaplan-Meier curves will be provided, when appropriate, for time from first dose of study treatment to the first occurrence of selected TEAEs as well as incidence rates at 24, 48, 72, and 96 weeks of exposure. Patients without any event will be censored at the end of the TEAE period. Selected TEAEs could be AESIs (e.g. neurocognitive events), or TEAE related to any clinically significant signal that needs further characterization;

- The frequency of selected AEs by SOC and PT over time during the treatment period (number of patients experiencing AE and percentage by patient-months) will be provided by time intervals defined as: ≤ 24 weeks, >24 to ≤ 48 weeks, >48 to ≤ 72 weeks, >72 to ≤ 96 weeks, using the PROC LIFETEST with the actuarial method. Only the first event will be counted.

Analysis of all treatment emergent serious adverse event(s)

- All serious TEAEs by primary SOC, HLT, HLT, and PT and by SOC/PT; Patient listings of serious TEAEs will be provided for the report appendix.
- All serious TEAEs by treatment group regardless of relationship in one column and in the same table a second column with TEAEs related to alirocumab according to investigator's opinion, by primary SOC, HLT, HLT, and PT;
- The event rate per patient-year will be provided for all serious TEAEs by SOC and PT.

Analysis of all treatment-emergent adverse event(s) leading to treatment discontinuation

- All TEAEs leading to permanent treatment discontinuation, by primary SOC, HLT, HLT, and PT and by SOC/PT; Patient listings of TEAEs leading to permanent treatment discontinuation will be provided for the report appendix.

Analysis of groupings of adverse events including selected adverse events of special interest

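### SAP 5.5.1 plots the incidence of discontinuation due to AEs by Kaplan-Meier with no rule for other stops; censoring them would overstate the share of patients who stop for an AE

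*SAP*

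**What the plan says.** SAP 5.5.1 plans two curves by arm in the safety population. The first is "The incidence of premature study treatment discontinuation (irrespective of the reason"), and the second is the AE-specific one: "premature treatment discontinuation due to AEs will be presented graphically by treatment group in the safety population using the Kaplan-Meier method". The section does not say how a patient who stops for another reason, or dies, enters the AE curve, and it plans no cumulative incidence function. For other Kaplan-Meier displays the SAP does state when event-free patients are censored: at the end of the TEAE period in 5.7.1, and at the end of the treatment period in 5.8.

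Crude figures are planned as well. SAP 4.4 and 5.4 give discontinuations by main reason. SAP 5.7.1 gives the number and percentage of patients with a TEAE leading to permanent discontinuation, and then "All TEAEs leading to permanent treatment discontinuation, by primary SOC, HLT, HLT, and PT and by SOC/PT".

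Protocol 7.3.1.2 lists reasons for permanent discontinuation that need not be AEs, such as patient request, sponsor request and intention for pregnancy. Protocol 9.5.2.6 adds an optional analysis of the same kind: "Time to liver-related treatment discontinuation and time to liver death may also be provided". The SAP's own section on liver injury (5.7.2) does not take it up.

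The only attrition figures are in the sample-size text (SAP 2.2; Protocol 9.2): "Assuming dropout rate of 20% in the first year and 25% in the second year". They are not described as drug-discontinuation rates and are not split by reason.

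**The concern.** A patient who has already stopped drug at their own request cannot later stop it because of an AE. Kaplan-Meier with such patients censored assumes that they would have gone on to stop for AEs at the same rate as those still on drug. The result describes a hypothetical setting in which nobody stops for any other reason. It is not the share of randomized and treated patients who stop for an AE, which is what a curve labelled incidence is read as showing.

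Tolerability is a secondary objective, and this graph shows AE discontinuation over time. If other stops are censored, its week 96 height will lie above the crude percentage in the safety tables, and a reader will have to work out why. The gap also grows with the number of non-AE stops in an arm, so two arms with the same proportion stopping for AEs can show different curves. Because the rule is unstated, two programmers could produce different graphs. Censoring at the stop gives the upward bias; keeping non-AE stoppers in the risk set to week 96 would come close to the cumulative incidence.

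**Working it through.** **1. Reproduce the plan's figures to establish cumulative attrition.** The inputs are in SAP 2.2: "This sample size is based on the noninferiority margin of 0.2 for the primary outcome measure"; "the assumed mean difference between the treatment groups is 0 and the standard deviation is 1.0"; "To achieve 95% power using a 2-sided 95% confidence interval (CI) approach (2-sided alpha=0.05").

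- Normal approximation: n = 2 × (1.960 + 1.645)² × 1.0² / 0.2², which rounds up to 650 per arm. The noncentral t gives 651 (power 0.9501), the plan's figure.
- Inflation: 651 / (0.80 × 0.75) = 651 / 0.60 = 1085, the plan's figure. Adding the rates would give 651 / 0.55 = 1184, so the plan compounds them.
- Cumulative loss is therefore 1 − 0.60 = 40%.

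**2. Inputs the documents do not give (assumptions).**

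- Total drug discontinuation: 40% as a proxy, with 20% as an alternative.
- AE share of all stops, s: 5-50%.
- Timing of AE stops relative to other stops: proportional, early or late.
- Handling of other stops: censored at the stop.

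**3. Proportional timing, 40% total.** The all-cause cumulative hazard is −ln(0.80) − ln(0.75) = −ln(0.60) = 0.511. With AE share s:

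- true cumulative incidence = 0.40 × s
- 1-KM = 1 − 0.60^s
- relative excess = (1 − 0.60^s) / (0.40 × s) − 1

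| AE share s | True incidence | 1-KM | Excess (points) | Relative excess |
|---|---|---|---|---|
| 5% | 2.0% | 2.5% | 0.5 | +26% |
| 10% | 4.0% | 5.0% | 1.0 | +24.5% |
| 15% | 6.0% | 7.4% | 1.4 | +23% |
| 25% | 10.0% | 12.0% | 2.0 | +20% |
| 40% | 16.0% | 18.5% | 2.5 | +15.5% |
| 50% | 20.0% | 22.5% | 2.5 | +13% |

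A simulation at s = 20% gave +21.5%, against +21.4% from the formula.

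**4. Vary the timing (40% total, AE incidence 4-10% unless noted).** With AE shares s1 and s2 in years 1 and 2, incidence = 0.20 × s1 + 0.80 × 0.25 × s2, and 1-KM = 1 − 0.80^s1 × 0.75^s2. For example, take AE incidence 4% with three quarters of it in year 1. Then s1 = 0.03/0.20 = 0.15, s2 = 0.01/0.20 = 0.05, and 1-KM = 4.67%, an excess of +17%.

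| AE stops | Relative excess |
|---|---|
| 75% in year 1 | +13% to +17% |
| 90% in year 1 | +8% to +12% |
| All in year 1 | +6% to +9% |
| All in first 24 weeks (AE incidence 4% and 8%) | +3% to +5% |
| 75% in year 2 | +27% to +32% |

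**5. Lower total discontinuation (20%, proportional timing).** The excess is (1 − 0.80^s) / (0.20 × s) − 1: +10% at s = 10%, +8.5% at 25% and +6% at 50%.

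**6. Unequal non-AE stopping between arms (assumed).** Let 6% stop for AEs in both arms, with 24% and 34% stopping for other reasons. Totals are 30% and 40%, and AE shares are 0.20 and 0.15. The curves end at 1 − 0.70^0.20 = 6.9% and 1 − 0.60^0.15 = 7.4%.

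**The case against.** Four points can be made for leaving the section alone.

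- **The SAP does not say that other stops are censored.** This is right. Censoring is an inference from the method's name, and the firm defect is a missing rule. But the usual implementation is the biased one, and either reading calls for the same edit.

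- **The dropout rates are not discontinuation rates.** Protocol 7.3.1 asks patients who stop drug to stay in the study, so 40% is only a proxy. It is not unreasonable, because the primary analysis uses scores only up to 70 days after the last injection (SAP 4.6.1, 5.6.1). Patients off drug for longer than that supply no week 96 primary value. A reader might combine the stated rates with the method and infer a 20-25% overstatement fixed by the plan itself. The documents do not support that. The band needs all of the 40% to be drug discontinuation, an AE share of about 8-25%, and similar timing of AE and other stops; the plan states none of these.

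- **The crude percentages are already planned and nothing is tested on this graph.** This stands and limits the harm. A 1-KM curve lying above a crude percentage is a difference in what is estimated, not a contradiction between tables. The between-arm artefact in step 6 is 0.5 points, against a between-arm standard error of about sqrt(2 × 0.06 × 0.94 / 1085) = 1.0 point. The crude figures do not, however, repair the curve over time.

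- **The choice is partly one of estimand.** With equal AE hazards and independent causes, Kaplan-Meier is unaffected by unequal non-AE stopping, while the cumulative incidence is not. At an AE cumulative hazard of 0.077 in both arms and 24% against 34% other stops, the cumulative incidence ends at about 6.4% and 6.0%. This is a real caveat on reading the new curve. It does not rescue the present one, which the SAP labels an incidence.

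**Conclusion.** The point holds in a limited form. SAP 5.5.1 leaves the handling of non-AE stops unstated for a curve presented as the incidence of AE discontinuation. Under the usual censoring the curve lies above the true proportion in every scenario examined. The direction is secure; the size depends on total discontinuation, AE share and timing, none of which the documents give. At 40% total with similar timing and AE shares of 5-50%, the excess is 13-26% relative (0.5-2.5 points). Across the other scenarios it runs from about 3% to 32%.

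The all-cause curve has no competing cause of discontinuation and needs no change. The noninferiority conclusion and the crude safety tables are unaffected. The change is worth making because it costs little, but no trial conclusion depends on it.

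**What to change.** In SAP 5.5.1:

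- Keep Kaplan-Meier for discontinuation for any reason.
- For discontinuation due to AEs, plot the Aalen-Johansen cumulative incidence by arm. Discontinuation for non-AE reasons, including death not attributed to an AE, is the competing event. Stops due to fatal AEs count as AE discontinuations, so that they do not leave the AE curve. Completion of treatment is censoring.
- Apply the same rule to liver-related treatment discontinuation only if that optional analysis is produced.

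The cost is a short SAP edit and one programming change, with no new data. The report has one more estimator to describe. The height of the new curve will depend on non-AE stopping in each arm, so it should be read beside the all-cause curve.

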5.5.2. Measurement of Compliance

Study treatment compliance parameters will be descriptively summarized using the number of patients with data, mean, SD, median, minimum and maximum for the variables listed in Section 4.5. According to protocol, cases of overdose are reported in the AE e-CRF pages and will be described in the AE analysis.

Both monitored and derived protocol deviations will be summarized for important deviations (counts of deviations), patients (incurring a deviation by count and percentage), and by type of important deviation (patient count and percentage). A patient listing of all major and minor protocol deviations will be provided.

5.6. Analyses of Primary and Secondary Endpoints

5.6.1. Analyses of Primary Neurocognitive Variable

The primary neurocognitive analysis is a statistical evaluation of the noninferiority of the Praluent 75 mg Q2W/up-titrate 150 mg Q2W dose regimen to placebo for the primary endpoint of change in SWM strategy z-score from baseline to week 96 in the primary safety population. The 2-sided 95% CI for the mean treatment difference at week 96 will be determined using an appropriate contrast statement in a mixed-effect model with repeated measures (MMRM). The upper CI limit will be compared to the noninferiority margin which is defined as 0.2 and the noninferiority will be declared if the upper CI limit is below the noninferiority margin.

In the case noninferiority is achieved for the primary neurocognitive function endpoint comparison, superiority of the primary neurocognitive function endpoint will be assessed using the same upper CI limit calculated for the primary comparison. Specifically, the upper CI limit will be compared to zero and superiority will be declared if the upper CI limit is below zero. A statistical multiplicity adjustment is not needed, since this process of noninferiority achievement followed by superiority assessment using the same 95% upper CI limit on the primary endpoint corresponds to a simple closed test procedure (EMA/CPMP/EWP/482/99 – 27July 2000).

The MMRM model will include the fixed categorical effects of treatment group (placebo, Praluent), both randomization strata (as per IVRS/IWRS), time point (weeks 24, 48, 72, and 96), treatment-by-time point interaction, and strata-by-time point interaction, as well as the continuous covariate of baseline SWM strategy raw score value and baseline value-by-time point interaction. Post-baseline assessments within a patient's TEAE period will be included in the analysis and missing data are accounted for by the MMRM model. Model assumptions for normality will be explored prior to the analysis testing.

This model will be run using Statistical Analysis Software (SAS) mixed procedure with an unstructured correlation matrix to model the within-patient errors. Parameters will be estimated using restricted maximum likelihood method with the Newton-Raphson algorithm. Denominator degrees of freedom will be estimated using Satterthwaite's approximation.

This model will provide baseline adjusted least-squares means estimates at week 96 for both treatment groups with their corresponding standard errors.

To support the clinical interpretation of the primary neurocognitive analysis, the SWM strategy raw score change from baseline to week 96 in the primary safety population will also be provided using the MMRM analysis method described above (at least includes least squares mean and 95% CI).

Model Assumption Checks

Homogeneity of treatment effect across baseline SWM strategy z-score

In order to check the homogeneity of treatment effect versus baseline SWM strategy z-score, the following interaction terms will be added in the primary MMRM model:

- Treatment group * baseline SWM strategy z-score
- Treatment group * time-point * baseline SWM strategy z-score

Within the framework of this model with interaction terms, a graph presenting the LS means difference versus placebo at week 96 and the corresponding 95% CI will be provided by baseline SWM strategy z-score value.

Analysis of residuals:

The analysis of the residuals of the MMRM will be primarily based on studentized residuals. It will include:

- Normality of studentized residuals, presented graphically using histogram and QQ-plot.
- Plot of studentized residuals versus predicted values.
- Distribution of studentized residuals, presented graphically using boxplots, within each category of the fixed categorical effects of the MMRM:
 - treatment group (Praluent, placebo)
 - time point (weeks 24, 48, 72, and 96)
 - treatment-by-time point interaction
 - randomization strata
 - randomization strata-by-time point interaction.

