2. INVESTIGATING PLAN

2.1. Study Design and Randomization

This is a randomized, double-blind, placebo-controlled trial to evaluate neurocognitive function in patients with Heterozygous familial hypercholesterolemia (heFH), or in non-familial hypercholesterolemia (non-FH) patients, at high or very high cardiovascular risk.

Patients will be randomized in a 1:1 ratio to receive either placebo or 75 mg Praluent Q2W. Randomization will be stratified by age (<65 or \geq 65) and by statin use (no statin, low lipophilicity of the concomitant statin, or high lipophilicity of the concomitant statin).

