10.5. Detailed Description of the Multiple Imputation Procedure

The following is a detailed description of the multiple imputation procedure which will be used for sensitivity analysis of primary endpoint as well as the analysis of the secondary endpoints.

In general, the missing pattern is anticipated to be not monotone, a two-step approach will be used:

- Step 1: the MCMC method will be used in conjunction with the IMPUTE=MONOTONE option to create an imputed data set with a monotone missing pattern.

- Step 2: Using the monotone data set from step 1, missing data will be imputed using the regression method.

The imputation model for step 1 will include the treatment group and the values of the analyzed parameter at baseline and planned time-points up to week 96.

The imputation model for step 2 will include the same variables as in step 1 with the following additional variables:

- the randomization strata (age and statin use strata);
- age, BMI, and gender (age and BMI included as continuous variables).

Non-continuous variables included in the imputer's model (i.e., treatment group, randomization strata and gender) are not expected to be missing.

In addition, for continuous efficacy variables anticipated to have a non-normal distribution (i.e. TG and Lp(a)), data will be log-transformed before imputation process and then back-transformed to create the imputed data sets using the TRANSFORM statement of SAS MI procedure.

For variables other than those continuous efficacy variables anticipated to have a non-normal distribution (i.e. TG and Lp(a)), for each simulation leading to negative imputed value, another value will be redrawn using MINIMUM option of MI SAS procedure.

The number of imputations (100) will be informally verified by replicating sets of 100 imputations and checking whether the combined results are stable. If not stable, the number of imputations will be increased and informally checked as above, and thus continued until stable estimates are obtained.

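### The primary MMRM could adjust for exact age as well as the age stratum: a small, almost free improvement, not an error

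*SAP*

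**What the plan says.** SAP 5.6.1 lists the terms of the primary MMRM: treatment, "both randomization strata (as per IVRS/IWRS", time point, treatment-by-time, strata-by-time, baseline SWM strategy raw score and baseline-by-time. Protocol 9.5.2.1 specifies the same model. Protocol 9.1 defines the age stratum as two levels cut at 65, and protocol 4.2.1 admits patients from 40 to 85. Age therefore enters as two bands about 25 and 20 years wide.

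SAP 4.1 lists age in years as a quantitative variable. SAP 10.5 describes a two-step imputation for the same endpoint. Step 1 uses treatment group and the scores only. Step 2 adds the randomization strata and "age, BMI, and gender (age and BMI included as continuous variables".

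The ANCOVA run on the imputed data (SAP 5.6.1.2) goes back to treatment, strata and baseline score. The stratification sensitivity analysis (SAP 5.6.1.1) replaces IVRS/IWRS strata with e-CRF strata, so age stays at two levels. The pattern-mixture draws (SAP 10.6) have no age term. No planned analysis model for the primary endpoint adjusts for exact age, and no reason is given.

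**The concern.** Cognitive scores may well depend on age, and age may well affect who stays for 96 weeks. A two-level term leaves all age variation inside each band in the residual, which costs some precision.

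The second matter is missing data. SAP 5.6.1.2 says that the MMRM relies on data being missing at random, and in this model that means given its covariates and the observed scores. The plan expects 40% dropout by week 96. If dropout depends on exact age within a band, the primary model captures that only through scores already observed. What is at stake is a slightly wider interval and, under a condition set out below, a small bias in the contrast that is compared with the margin.

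**Working it through.** **1. The plan's own figures.** SAP 2.2 states: "To achieve 95% power using a 2-sided 95% confidence interval (CI) approach (2-sided alpha=0.05"; a "noninferiority margin of 0.2 for the primary outcome measure"; and "the assumed mean difference between the treatment groups is 0 and the standard deviation is 1.0". Allocation is 1:1 (SAP 2.1).

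- n per group = 2 × SD² × (1.960 + 1.645)² / margin² = 2 × 12.996 / 0.04, about 650 by the normal approximation. The noncentral-t calculation gives 651 (power 95.01%), as the SAP says: "the sample size is calculated to require 651 patients per treatment group".
- For the inflation to the randomized number, the SAP's basis is "Assuming dropout rate of 20% in the first year and 25% in the second year". That gives retention of 0.80 × 0.75 = 0.60, and 651 / 0.60 = 1085.

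Both figures reproduce, and neither depends on how age is modelled.

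**2. How much of age the stratum captures.** The age distribution is not given, so these are assumptions.

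- Uniform over 40 to 85, cut at 65: p = 25/45 = 0.556. The band means are 52.5 and 75. Between-band variance = 0.556 × 0.444 × 22.5² = 125. Total variance = 45²/12 = 168.75. Captured: 125/168.75 = 74%; left over: 26%.
- Normal, cut at the median: captured 2/π = 64%; left over: 36%.
- Normal truncated to 40 to 85, means 58 to 65 and SDs 8 to 10: left over 34% to 50%. The 50% case has mean 58, SD 8 and only 19% of patients aged 65 or over.

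**3. Precision.** Let R² be the share of week 96 variance that age explains after baseline score (assumed), and w the share of age variance left inside the bands. The further fall in residual variance from exact age is R²w / (1 − R²(1 − w)).

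- R² = 2%, w = 26%: 0.0052/0.9852 = 0.5%; SE falls 0.3%.
- R² = 10%, w = 36%: 0.036/0.936 = 3.8%; SE falls 1.9%.
- Extreme case, R² = 10%, w = 50%: 0.05/0.95 = 5.3%; SE falls 2.7%.

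On the plan's scale, with 1.0 taken as the residual SD of the two-level model, the interval half-width is 1.96 × √(2/651) = 0.1086. With w of 36% to 42%, a partial correlation of 0.1 (R² = 1%) brings it to 0.1084, with 649 evaluable patients needed. A correlation of 0.3 (R² = 9%) brings it to 0.1064 to 0.1068, with 626 to 629 needed. Power at 651 moves from 95.0% to about 95.1% and 95.7% respectively.

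**4. Bias.** Four-visit trials with monotone dropout were simulated: 2170 patients, about 60% retained, no true treatment effect, 1500 replicates, Monte Carlo error 0.0011. Ages were normal (mean 62, SD 9) within 40 to 85. The fit was the maximum-likelihood equivalent of an unstructured MMRM with baseline score and age stratum, without and with continuous age; the statin stratum was left out. The age effect is in score units at week 96 per SD of age. Cells show mean error with two-level age / with continuous age added.

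| Dropout odds ratio per SD of age, placebo / Praluent | Age effect 0.05 | Age effect 0.1 | Age effect 0.2 |
|---|---|---|---|
| 1.0 / 1.0 | −0.0006 / −0.0006 | +0.0027 / +0.0027 | −0.0010 / −0.0007 |
| 1.5 / 1.5 | −0.0018 / −0.0019 | +0.0007 / +0.0007 | 0.0000 / −0.0001 |
| 1.0 / 1.5 | −0.0012 / +0.0014 | −0.0063 / −0.0012 | −0.0087 / +0.0019 |
| 1.0 / 2.0 | −0.0017 / +0.0026 | −0.0089 / −0.0006 | −0.0168 / −0.0001 |
| 0.67 / 1.5 | −0.0076 / −0.0018 | −0.0136 / −0.0019 | −0.0197 / +0.0025 |

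With equal age-related dropout, the two models agree and neither shows systematic bias. With unequal dropout, the two-level model is off by about 0.001 to 0.020, at most 0.0197/0.2 = 10% of the margin, while the continuous-age model stays within 0.003 of zero. Lower scores are better, so the negative sign favours noninferiority. It arises here because older patients worsen more and leave Praluent more often.

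**The case against.** A reader might infer that the primary analysis violates missing-at-random, or that the MMRM and the imputation contradict each other. The documents support neither. Age that predicts both decline and dropout does not by itself bias the treatment difference; age-related dropout must also differ between arms, and nothing in the documents suggests that it will. Baseline-by-time and earlier scores under an unstructured covariance also absorb part of any age effect.

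Putting more predictors in an imputation model than in the analysis model is ordinary practice. SAP 5.6.1.2 presents multiple imputation as a robustness check by a different method, and because step 2 conditions on exact age, it is a partial safeguard against this very concern. The same section compares baseline characteristics between patients with and without a week 96 score, and adds a pattern-mixture analysis for data not missing at random.

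It is also tempting to say that adding age would give the MMRM and the imputation one common set of covariates. It would not: BMI and gender stay in the imputation only, and step 1 has no age term.

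All of this stands, and so does the remark that the change is not wholly without cost. What remains is that the decision rests on the MMRM, which leaves out a collected and plausibly prognostic baseline variable.

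**Conclusion.** The point holds as a low-cost improvement, not as a defect. The plan's model is valid as written, and the sample sizes of 651 and 1085 stand.

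The expected gain is a fall of about 0.5% to 4% in residual variance, and about 2% or less in standard error, if age explains 2% to 10% of week 96 variance after baseline score. An age distribution concentrated below 65 would push the top of that range slightly higher. The protection against bias is worth about 0.001 to 0.020 z-score units, and only where age-related dropout differs by arm. With equal age-related dropout there is nothing to protect against.

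The age effect, age distribution and dropout odds ratios are all assumptions, because the documents give none of them.

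**What to change.** In SAP 5.6.1, add continuous age and age-by-time point to the primary MMRM, keeping both randomization strata and their time interactions. Do the same in the exploratory CANTAB MMRMs (SAP 5.6.2), and add continuous age to the ANCOVA after imputation (SAP 5.6.1.2).

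Protocol 9.5.2.1 specifies the current model, so record and justify the departure in SAP 1.2.3, which now reports no modifications from the protocol. SAP section 1 allows revisions before database lock and while treatment remains blinded. If the sponsor prefers to leave the primary model alone, prespecifying the age-adjusted MMRM as a sensitivity analysis would recover most of the benefit.

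The cost is a few lines of SAP text, an age slope at each of the four visits (four more parameters), and the assumption that age acts linearly at each visit alongside a correlated age stratum. No new data are needed.
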